### 9.2.2.2. Pharmacokinetics Analyses

#### Pharmacokinetic Parameters

To assess the pharmacokinetics of PF-06650808 (ADC), PF-06460005 (total antibody) and PF-06380101 (unconjugated payload), the PK parameters detailed in [Section 7.3](#) will be listed and summarized for subjects in the PK analysis set (as defined in [Section 6.4](#)). Missing values will be handled as detailed in [Section 8](#). Each PK parameter will be summarized by dose and cycle and will include the set of summary statistics as specified in the table below:

Parameter	Summary statistics
AUC last , AUC inf , AUC τ , C max , CL, V ss , and R ac	N, arithmetic mean, median, cv%, standard deviation, minimum, maximum, geometric mean
t 1/2	N, arithmetic mean, median, cv%, standard deviation, minimum, maximum
T max	N, median, minimum, maximum

There will be 1 summary table presenting all PK parameters. This will include data from all cohorts and will be summarized by dose group and cycle.

To assess the relationship between the PK parameters and dose, dose normalized AUCinf, AUClast, AUCτ, and Cmax will be plotted against dose (using a logarithmic scale), and will include individual subject values and the geometric means for each dose. Geometric means will have a different symbol than the individual values. The values will be dose normalized (to a 1 mg/kg dose) by dividing the individual values and raw geometric means by dose. A footnote will be added to the plots to indicate that geometric means are presented are presented on the plot.

## **Pharmacokinetic Concentrations**

To assess the PK profile of PF-06650808 (ADC), PF-06460005 (total antibody) and PF-06380101 (unconjugated payload), PK concentrations will be listed, summarized and plotted for subjects in the PK analysis set (as defined in [Section 6.4](#)), where missing and BLQ values will be handled as detailed in [Section 8.3](#).

Presentations for PF-06650808 (ADC), PF-06460005 (total antibody) and PF-06380101 (unconjugated payload) will include:

- a listing of all concentrations sorted by dose, subject id, day and nominal time post dose. The listing of concentrations will include the actual times. Deviations from the nominal time will be given in a separate listing.
- a summary of concentrations by dose, day and nominal time post dose, where the set of statistics will include n, mean, median, standard deviation, coefficient of variation (cv) and the number of concentrations above the lower limit of quantification.
- a plot of mean concentrations against nominal time postdose by dose (based on the summary of concentrations by dose and time postdose), preferably with all doses also on the same graph.
- a plot of median concentrations against nominal time postdose by dose (based on the summary of concentrations by dose and time postdose), preferably with all doses also on the same graph.
- a log-linear plot of mean concentrations against nominal time postdose by dose (on the same plot), preferably with all doses also on the same graph.
- a log-linear plot of median concentrations against nominal time postdose by dose (on the same plot), preferably with all doses also on the same graph.
- plots of individual concentrations against actual time postdose.

The length of time used for the x-axes of these plots will be decided on review of the data, and will depend on how long PK concentration is quantifiable in the matrix.

In addition to the above, a median plot of the predose concentrations at each cycle against day will be provided for each dose, on the same plot, in order to assess the attainment of steady-state. Individual subject profiles will also be plotted.

For summary statistics and mean/median plots by sampling time, the nominal PK sampling time will be used, for individual subject plots by time, the actual PK sampling time will be used.

## **Population Pharmacokinetic Analysis or PK/PD Modeling**

*Pharmacokinetic and pharmacodynamic data from this study may be analyzed using compartmental or mixed-effect modeling approaches and may also be pooled with other study results. PK/PD modeling may be attempted to investigate any causal relationship between PF-06650808 exposure and biomarkers or significant safety endpoints. The results of these analyses, if performed, may be reported separately.*

CCI [REDACTED]

[REDACTED]

[REDACTED]

[REDACTED]

[REDACTED]

### **9.2.3. Safety Analyses**

#### **Adverse Events**

Adverse Events (AEs) will be graded by the investigator according to the CTCAE version 4.03 and coded using the MedDRA. The focus of AE summaries will be on Treatment Emergent Adverse Events, those with initial onset or increasing in severity after the first dose of study medication. The number and percentage of patients who experienced any AE, serious AE (SAE), treatment related AE, and treatment related SAE will be summarized according to worst toxicity grades. The summaries will present AEs both on the entire study period and by cycle (Cycle 1 and Cycles beyond 1). The Safety Analysis Set will be used.

#### **Laboratory Tests Abnormalities**

The number and percentage of patients who experienced laboratory test abnormalities will be summarized according to worst toxicity grade observed for each laboratory test. The analyses will summarize laboratory tests both in the entire study period and by cycle (Cycle 1 and Cycles beyond 1). The Safety Analysis Set will be used.

For laboratory tests without CTC grade definitions, results will be categorized as normal, abnormal or not done.

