4.1. Inclusion Criteria

Patient eligibility should be reviewed and documented by an appropriately qualified member of the investigator's study team before patients are included in the study.

Patients must meet all of the following inclusion criteria to be eligible for enrollment into the study:

1. For the dose escalation phase: Histological or cytological diagnosis of advanced/metastatic solid tumor that is resistant to standard therapy or for which no standard therapy is available.
2. For the dose expansion phase: Previously treated metastatic triple negative breast cancer that expresses Notch3 with at least one measurable lesion.
3. For the dose expansion phase: Archival core needle biopsy or prospectively collected core needle biopsy available for exploratory biomarker and Notch3 expression analysis.
4. Age ≥ 18 years.
5. ECOG Performance Status (PS) of 0 or 1.
6. Life expectancy ≥ 12 weeks.
7. Adequate Bone Marrow Function as defined by:

Absolute Neutrophil Count (ANC) $\geq 1,500/\text{mm}^3$ or $\geq 1.5 \times 10^9/\text{L}$;

Platelets $\geq 100,000/\text{mm}^3$ or $\geq 100 \times 10^9/\text{L}$;

Hemoglobin ≥ 9 g/dL.

8. Adequate Renal Function as defined by:
 - a. Serum creatinine $\leq 1.5 \times$ upper limit of normal (ULN); or
 - b. Estimated creatinine clearance ≥ 60 ml/min as calculated using the method standard for the institution.
9. Adequate Liver Function as defined by:

- a. Total serum bilirubin $\leq 1.5 \times$ ULN unless the patient has documented Gilbert syndrome;
- b. Aspartate and Alanine Aminotransferase (AST & ALT) $\leq 2.5 \times$ ULN; $\leq 5.0 \times$ ULN if there is liver involvement secondary to tumor;
- c. Alkaline phosphatase $\leq 2.5 \times$ ULN; ($\leq 5 \times$ ULN in case of bone metastasis).

10. Recovery from all prior surgical or adjuvant treatment-related toxicities, to Baseline status, or a CTCAE Grade of 0 or 1, except for toxicities not considered a safety risk, such as alopecia. Post-surgical pain will not be considered a basis for exclusion.
11. Negative serum/urine pregnancy test (for females of childbearing potential).
12. Male and female patients of childbearing potential must agree to use a highly effective method of contraception throughout the study and for at least 28 days after the last dose of assigned treatment. A patient is of childbearing potential if, in the opinion of the investigator, he/she is biologically capable of having children and is sexually active.

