9.6.2.2. Laboratory tests abnormalities

The number and percentage of patients who experienced laboratory test abnormalities will be summarized according to worst toxicity grade observed for each laboratory assay. The analyses will summarize laboratory tests both on the entire study period and by cycle (Cycle 1 and Cycles beyond 1).

For laboratory tests without CTC grade definitions, results will be categorized as normal, abnormal or not done.

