#### **7.2.3. Laboratory Data**

The laboratory results will be graded according to the NCI CTCAE v4.03 severity grade. For labs for which an NCI CTCAE v4.03 scale does not exist, the frequency of subjects with values below, within, and above the normal ranges will be summarized by dose. Baseline evaluations for laboratory data are those collected:

- Within 28 days prior to Cycle 1/Day 1.
- Closest but prior to Cycle 1/Day 1 if there is more than one baseline evaluation.

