#### **Treatment Emergent Adverse Events**

- All deaths from start of treatment until 28 days after the final dose.

- All treatment related SAEs.
- All unrelated SAEs from treatment start until 28 days after final dose of treatment.
- All non-fatal AEs occurring after treatment start up until 28 days after final dose of treatment or until start of new anti-cancer treatment, whichever is first.
- Disease progression is not considered a treatment emergent adverse event unless the subject dies of disease prior to 28 days after discontinuation of treatment.
- Events that are continuations of baseline abnormalities are considered treatment emergent adverse events only if there is an increase in grade over baseline.

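### Laboratory abnormalities are tabulated by worst grade with no comparison to baseline, so unchanged entry abnormalities count as on-study findings, mainly in the lower grades

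*SAP*

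**What the plan says.** The analysis rule is in the laboratory part of SAP 9.2.3: "The number and percentage of patients who experienced laboratory test abnormalities will be summarized according to worst toxicity grade observed for each laboratory test". It is applied to the whole study and separately to Cycle 1 and to later cycles. Protocol 9.6.2.2 has the same rule: abnormalities are "summarized according to worst toxicity grade observed for each laboratory assay". Neither text mentions baseline, shift, change or worsening.

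Tests without a CTCAE grade are handled in two places, again without baseline. SAP 7.2.3 says "the frequency of subjects with values below, within, and above the normal ranges will be summarized by dose", and SAP 9.2.3 says "For laboratory tests without CTC grade definitions, results will be categorized as normal, abnormal or not done".

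SAP 7.2.3 does define a laboratory baseline: a value from the 28 days before Cycle 1 Day 1 and, where there are several, "Closest but prior to Cycle 1/Day 1 if there is more than one baseline evaluation". No laboratory table, listing or figure in the readable text refers to it.

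Elsewhere the SAP does compare with baseline. For adverse events, SAP 7.2.4 states: "Events that are continuations of baseline abnormalities are considered treatment emergent adverse events only if there is an increase in grade over baseline". For QTcF, SAP 7.2.5 plans change from baseline and a shift table of baseline against worst value.

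Protocol 4.1 admits AST and ALT up to 2.5 times ULN, or 5.0 times "ULN if there is liver involvement secondary to tumor". It also admits alkaline phosphatase up to 2.5 times ULN (5 times with bone metastasis), bilirubin up to 1.5 times ULN (with an exception for Gilbert syndrome), creatinine above ULN, and hemoglobin from 9 g/dL.

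**The concern.** A table of worst observed grade mixes two groups: patients whose laboratory value worsened after dosing, and patients who came in abnormal because of their disease or earlier treatment and stayed as they were. In advanced solid tumors with these entry limits, the second group will not be empty. A persisting entry abnormality is left out of the treatment-emergent adverse event tables but counted in the laboratory tables, so the two sets of results can disagree with no explanation in the report.

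Laboratory abnormalities are a named secondary endpoint (Protocol 2.2), and the study has no concurrent control arm. The comparison with the patient's own entry value is the most direct way to separate a new finding from an old one, and the plan leaves it out although it has already defined the value needed.

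**Working it through.** The plan states no figure on this point, so there is none to reproduce. The check has four steps.

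**1. Can an unchanged entry value enter the table?** Yes. Protocol 4.1 allows values above ULN for five chemistry tests, and SAP 9.2.3 counts the worst grade whether or not it is new. The CTCAE cut-offs are not printed in the documents (Protocol Appendix 4 points to the Study Manual and a website), so no exact entry grade is assigned here.

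**2. Which rows are safe?** Protocol 4.1 requires neutrophils of at least 1,500/mm³ and platelets of at least 100,000/mm³. The table in Protocol 5.2.6 gives Grade 4 as below 500/mm³ and below 25,000/mm³. Both are far below the entry floor, so Grade 4 neutropenia or thrombocytopenia cannot be an unchanged entry value. The entry limits suggest that the problem lies mainly in the lower grades.

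**3. Which sample is baseline?** The schedule of activities includes hematology and chemistry on Cycle 1 Day 1. SAP 9.2.4 takes Day 1 as the first dosing date of a cycle. SAP 7.2.3 takes the laboratory baseline from before Cycle 1 Day 1, whereas SAP 7.2.5 takes the ECG baseline from the pre-dose value on that day. Read literally, a pre-dose Day 1 blood sample is not baseline and can be summarised as a Cycle 1 result. Baseline would then always be a screening sample. Protocol 9.6 says that screening laboratory data used for eligibility stay out of the database unless otherwise noted, and Protocol 7.1.3 lets the Day 1 sample be skipped when screening was within 72 hours of dosing. For some patients the baseline may therefore not be in the database.

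**4. Illustration of size.** Let q be the share of patients abnormal on a given test at entry, with the abnormality persisting on treatment (assumed 10%, 30%, 50%). Let t be the share with a new or worsened grade, independent of q (assumed).

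- No worsening in anyone (t = 0): the row shows q × 20 in Part 2, which is 0.10 × 20 = 2, 0.30 × 20 = 6 and 0.50 × 20 = 10 patients. The count above baseline is 0.
- Some worsening (t = 20%): the worst-grade row shows q + (1 − q)t, and the excess over t is q(1 − t).

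| q | Worst-grade row | Above baseline | Excess of 20 | Excess of 55 |
|---|---|---|---|---|
| 10% | 28% | 20% | 1.6 | 4.4 |
| 30% | 44% | 20% | 4.8 | 13.2 |
| 50% | 60% | 20% | 8.0 | 22.0 |

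- Small dose groups: the chance that at least one of n patients enters abnormal on the test is 1 − (1 − q)^n. For n = 3, within the planned cohort size of 2 to 4, this is 27%, 66% and 88% for the three values of q. For n = 6, the minimum at the MTD, it is 47%, 88% and 98%.

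**The case against.** The best defence has three parts. First, the table matches the endpoint as Protocol 2.2 words it, which asks for the kind, frequency, grade and timing of abnormalities and not for change from baseline. The analysis is descriptive and tests no hypothesis. Second, laboratory findings that matter clinically become adverse events under Protocol 8.4, receive a causality assessment under 8.8, and count as treatment emergent only if the grade rises over baseline. Third, Part 1 escalates the dose, so results can also be compared across doses.

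All three limit the weight of the point, but none corrects the table. The adverse event rule does not govern the laboratory summaries and reaches only findings that meet the reporting criteria. Comparison across doses is weak in cohorts of 2 to 4, where one patient with an old abnormality changes the picture.

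A reader might infer more than the documents support:

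- That the recommended Phase 2 dose is put at risk. The Part 1 dose decision rests on first-cycle dose-limiting toxicities, judged event by event. Protocol 3.4 bases the recommended dose broadly on Phase 1 results, but no text routes this laboratory table into that choice.
- That the patient's own baseline is the only possible reference. Comparison across doses and causality assessment also exist.
- That a patient listed under both Cycle 1 and later cycles is counted twice. These are separate period summaries. The fault is that the split does not separate persisting from new abnormalities.
- That severe hematologic toxicity is inflated throughout. Step 2 of the working shows that this is not so for Grade 4 neutropenia and thrombocytopenia.

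**Conclusion.** The point holds. As written, the laboratory tables count unchanged entry abnormalities, and possibly pre-dose Day 1 values, as on-study findings, and the defined laboratory baseline has no use in any readable laboratory analysis. The effect lies mainly in the lower grades.

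Its size cannot be derived from the documents. The range of 2 to 10 of 20 Part 2 patients per test rests wholly on the assumed 10% to 50% entry share and on no change during treatment. It applies to one test at a time; the share of patients abnormal on any of several tests would be larger and must not be read into a single row.

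This is a flaw in how a descriptive secondary endpoint is presented. It does not undermine dose finding. It should be corrected because the SAP already applies the better rule to adverse events and QTcF. Whether baseline values are missing from the database is an open question, since Protocol 9.6 leaves room for exceptions.

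**What to change.** - **SAP 7.2.3:** define laboratory baseline as the last value before the first infusion, including a pre-dose Cycle 1 Day 1 sample, and exclude that value from all post-dose summaries.
- **SAP 9.2.3:** for each graded test, add a shift table of baseline grade by worst post-dose grade, and the number and percentage of patients with a grade above baseline, overall and by cycle group. The existing worst-grade table can stay beside them.
- **Protocol 9.6 and 7.1.3:** reconcile these with the SAP so that the screening value is entered in the database whenever it serves as baseline, in particular when the Day 1 sample is skipped.

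The cost is a few standard tables and one clarification of data capture. The sponsor should not assume that SAP wording alone is enough until it has confirmed that the screening values are captured. Nothing in treatment, visits or design changes.

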#### **Other Variables: Anti-PF-06650808 antibody**

For anti-PF-06650808 antibody, a listing, sorted by subject and study day, of the result of anti-PF-06650808 antibody screening (positive/negative [<1:negative]), the specificity, and titer will be listed. Summary counts of the patients, who are positive for the anti-PF-06650808, will be derived by study treatment and visit for the safety population. No summary statistics other than those cited above, will be generated.

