15. **Registration:** Patient number and dose level allocation will be provided by Pfizer Inc. Treatment should begin no longer than 3 days from registration.
16. **Study Treatment:** PF-06650808 will be administered once every 21 days as an infusion over approximately 60 minutes.
17. **Tumor Assessments:** Tumor assessments will include all known or suspected disease sites and may include chest, abdomen and pelvis CT or MRI scans. Brain scans and bone scans should be performed at baseline if disease is suspected and on-study as appropriate to follow disease. Baseline CNS imaging is not required with the exception of symptomatic patients to rule out CNS metastases. CT or MRI scans are to be done every 6 weeks (± 5 days) for the first two assessments (Week 6 and Week 12) and will then be collected every 12 weeks thereafter until disease progression by RECIST (v1.1) or death, or until permanent discontinuation of study treatment. Tumor assessments should be fixed according to the calendar, regardless of treatment delays. For patients enrolled in Part 2, responses of CR or PR must be confirmed by repeat assessment no more than 4 weeks after the criteria for response are first met. Tumor assessments should be repeated at the End of Treatment visit if more than 6 weeks have passed since the last evaluation.

CCI

19. **Anti PF-06650808 Antibodies:** Collection of serum to detect the presence of antibodies to PF-06650808 is to be obtained prior to the start of study drug infusion. Patients having an unresolved adverse event that is possibly related to anti-PF-06650808 antibodies at their last assessment will be asked to return to the clinic for ADA and drug concentration blood sampling at up to 3 month intervals until the adverse event or its sequelae resolve or stabilize at a level acceptable to the investigator and sponsor.

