7.6. Immunogenicity Evaluations

Assays to assess for anti-drug (anti-PF-06650808) antibodies (ADA) will be performed. All samples that are positive in a screening assay will be further characterized in terms of antibody specificity. Confirmed ADA responses may also be characterized for neutralizing antibodies (Nab). Patients found to have anti-PF-06650808 antibodies at their final study

visit and an ongoing AE possibly related to ADA will be asked to return to the clinic for ADA assessment at approximately 3 month intervals until the AE or its sequelae resolve or stabilize at a level acceptable to the investigator and sponsor.

Blood samples (6 mL) to provide approximately 5 mL of serum for ADA and Nab analysis will be collected into appropriately labeled tubes at times specified in the [Schedule of Activities](#). Details regarding the collection, processing, storage and shipping of the blood samples will be provided in the Study Manual.

Samples will be analyzed using a validated analytical method in compliance with Pfizer standard operating procedures.

CCI

[figure not shown]
. Samples collected for this purpose will be retained in accordance to local regulations and if not used within this timeframe, will be destroyed.

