9.5.3. Immunogenicity

The development of anti-PF-06650808 antibodies will be measured using validated assays. Listings and summary tabulations of the anti-PF-06650808 antibody data at baseline and post randomization will be generated.

Potential impact of immunogenicity on PK and clinical responses including PD markers, safety/tolerability and efficacy of PF-06650808 will be explored, if data is warranted.

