### **6.3. Safety Analysis Set**

*The safety analysis set includes all enrolled patients who receive at least one dose of study medication.*

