#### **7.2.6. Immunogenicity**

Anti-PF-06650808 antibody data will be collected at baseline and post-randomization according to the protocol.

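### The SAP limits the antibody summary to by-visit counts of positive patients and bars any other statistic, so no planned summary shows how many patients developed antibodies on treatment, and the bar conflicts with Protocol 9.5.3

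*SAP*

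**What the plan says.** SAP 9.2.3, in its paragraph on anti-PF-06650808 antibody, plans two outputs. The first is a listing by subject and study day, in which "the result of anti-PF-06650808 antibody screening (positive/negative [<1:negative]), the specificity, and titer will be listed". The second is the summary: "Summary counts of the patients, who are positive for the anti-PF-06650808, will be derived by study treatment and visit for the safety population". The paragraph closes: "No summary statistics other than those cited above, will be generated".

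On timing, SAP 7.2.6 says "Anti-PF-06650808 antibody data will be collected at baseline and post-randomization according to the protocol" (the study is not randomized, so this must mean after baseline). The protocol's Schedule of Activities, in its note on these antibodies, says "Collection of serum to detect the presence of antibodies to PF-06650808 is to be obtained prior to the start of study drug infusion". A pre-treatment result should therefore exist for each patient.

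On the population, SAP 6.3 says "The safety analysis set includes all enrolled patients who receive at least one dose of study medication". An ADA sample is not required.

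On the assay, Protocol 2.2 describes a tiered approach of screening, confirmation and titer, and Protocol 7.6 says "All samples that are positive in a screening assay will be further characterized in terms of antibody specificity".

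On use of the results, Protocol 9.5.3 plans tabulations at baseline and afterwards. It adds "Potential impact of immunogenicity on PK and clinical responses including PD markers, safety/tolerability and efficacy of PF-06650808 will be explored", on condition that the data warrant it.

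**The concern.** The clinical question is how many patients developed antibodies on the drug, and whether those patients had different exposure or outcomes. The planned summary answers neither part, and its last sentence tells the programmer to add nothing.

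Four gaps stand out. A count at a later visit mixes patients who were positive before dosing with those who became positive. Counts by visit cannot be turned into counts of patients. No number tested and no denominator is given, although patients leave treatment at progression or toxicity, so a falling count may only mean fewer samples. The text also does not say which assay tier makes a patient positive.

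The SAP treats its other safety data differently. SAP 7.2.4 has an explicit treatment-emergent rule for adverse events that refers back to baseline. SAP 9.2.3 summarizes adverse events and laboratory abnormalities as numbers and percentages of patients over the whole study. SAP 9.1 promises exact 95% intervals for binary endpoints. None of this reaches ADA.

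**Working it through.** The documents state no ADA rate, baseline prevalence or sampling rate, so there is no figure of the plan's to reproduce. The one related figure agrees: 35 patients at most in Part 1 plus about 20 in Part 2 gives 35 + 20 = 55.

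**1. What by-visit counts determine (no rates assumed).** If the counts at visits are c1, c2, ..., the number of patients ever positive lies between max(c) and sum(c).
- Counts 1, 2, 2, 1: between max = 2 and 1 + 2 + 2 + 1 = 6 patients ever positive.
- Two positive at baseline and two at Cycle 2: 0 newly positive if they are the same two patients, 2 if they are different.

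The same table is therefore compatible with no treatment-induced antibody and with two cases.

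**2. Pre-existing antibody (assumed inputs).** Take N = 55, 10% positive at baseline and staying positive, 10% of the rest becoming positive, and everyone sampled. Counts are rounded to whole patients.
- Baseline positive: 0.10 × 55 = 5.5, taken as 6. Baseline negative: 55 − 6 = 49.
- Newly positive: 0.10 × 49 = 4.9, taken as 5.
- Any positive after dosing: (6 + 5)/55 = 11/55 = 20.0%.
- Treatment-induced: 5/49 = 10.2%, exact 95% CI 3.4 to 22.2.

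For Part 2 alone (N = 20, 2 positive at baseline, 2 newly positive): 4/20 = 20.0% against 2/18 = 11.1% (1.4 to 34.7).

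**3. Denominator (assumed inputs).** Take N = 55, 20% with no post-baseline sample, and none positive at baseline.
- Sampled: 55 − 11 = 44. Newly positive: 0.10 × 44 = 4.4, taken as 4.
- 4/55 = 7.3% if a reader divides by the safety set; 4/44 = 9.1% (2.5 to 21.7) among those sampled.

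At a late visit with 2 positives and 10 of 20 patients still sampled: 2/20 = 10% against 2/10 = 20%.

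**4. Range.** With N = 55, baseline positivity of 0, 5 or 10% and unsampled patients at 0, 10, 20 or 30%, the crude figure on the safety set runs from 7.3% to 20.0%. The treatment-induced figure stays between 9.1% and 11.4%. The two departures pull in opposite directions, so the crude figure has no predictable bias.

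**5. The two texts on impact, side by side.** Protocol 9.5.3 says impact on PK, PD markers, safety and efficacy will be explored if the data warrant. SAP 9.2.3 bars any ADA summary statistic beyond the listing and the counts. SAP 9.2.5, on additional analysis, is marked not applicable. No visible section of the SAP describes an analysis by ADA status.

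**The case against.** The strongest defense is that a listing plus counts is a legitimate descriptive choice in a Phase 1 study with no hypotheses, about 55 patients and typically 2 to 4 per dose. The listing gives each patient's result by study day, with specificity and titer, so newly positive patients can be counted by hand. That stands as a reason not to overrate the point. It does not supply a prespecified definition or table, and the exclusion sentence forbids adding the table later.

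A reader might also infer three stronger things, which the documents do not support:

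- *That pre-existing antibody is reported as drug-induced.* The SAP labels no positive result that way. A pre-treatment sample is taken, and baseline should be its own row in a by-visit table. The gap is only that later rows do not separate old from new positives.
- *That unsampled patients dilute the rate.* The SAP plans counts, not a rate. Percentages such as 2/20 arise only if someone divides by the safety set. The defect is an unspecified denominator.
- *That the impact analysis is ruled out.* It is conditional in the protocol, and SAP 2 says the SAP supplements the protocol. SAP 4.2.2 allows optional work relating PK, safety and efficacy, and SAP 7.2.6 files immunogenicity under safety endpoints. Parts of the SAP are redacted and cannot be counted as missing. The analysis is absent from the visible text and in conflict with the exclusion sentence, no more.

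Nor does the SAP say that the counts use screening results. It leaves this open.

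**Conclusion.** The point holds as a gap in the summary and a conflict between two texts. Followed as written, no planned summary gives per-patient or treatment-induced ADA incidence for a secondary objective of both parts, and the exclusion sentence cannot be reconciled, on a literal reading, with Protocol 9.5.3.

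That by-visit counts fail to determine patient numbers is a matter of logic and needs no assumption. The percentages are illustrations: they rest on an assumed 10% treatment-induced rate, 0 to 10% positive at baseline with persistence, and 0 to 30% unsampled. Under those inputs the crude figure can be about twice the treatment-induced one or somewhat below it.

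This is worth correcting before analysis, because the SAP states a restrictive rule and is not merely silent. It does not threaten the primary endpoints.

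**What to change.** Rewrite the antibody paragraph in SAP 9.2.3 as follows:

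- Define positive as confirmed positive.
- Report baseline prevalence among patients with a baseline sample.
- Define treatment-induced ADA per patient as negative at baseline with any confirmed positive after dosing. Report n/N with an exact 95% interval overall, and descriptively by dose, among baseline-negative patients with at least one post-dose result.
- Keep the by-visit counts and show the number tested at each visit.
- Report boosted ADA only if a titer threshold is prespecified from the assay; the documents give none.
- Replace the exclusion sentence with a descriptive summary of ADC and total-antibody exposure by ADA status, to be produced if enough patients are positive. This brings the SAP into line with Protocol 9.5.3.
- Replace post-randomization with post-baseline in SAP 7.2.6.

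The samples are already being collected. The cost is SAP wording and a few extra descriptive tables. Numbers per dose will be small and intervals wide, so the overall figure will carry most of the information.
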